This is a single-center, prospective cohort study of subjects undergoing clinically indicated PET/CT MPI, with documented coronary artery disease or an intermediate to high pretest likelihood of coronary artery disease. Following the clinical study, the research study is explained to the subjects. Consenting subjects will return on another day (next calendar day or later) for a repeat stress study with Lexercise or a repeat Lexiscan stress PET. Approximately 50 subjects (not more than 16 patients with normal Rubidium-82 or N-13 ammonia PETMPI, 10 healthy volunteers and 24 patients with reversible perfusion defects) will be enrolled in this study. After successful screening and enrollment, 13 random subjects (8 normal and 5 ischemic) will return for repeat Lexiscan PET, and 37 subjects will return for a Lexercise PET/CT MPI. Lexiscan PET will be performed per standard protocol. For Lexercise, a symptom limited exercise treadmill study with Lexiscan injection at peak exercise is performed. Rubidium-82 or N-13 ammonia will be injected and PET/CT images will be obtained in a list mode acquisition. Images will then be unlisted and myocardial blood flow computed.

Number of Subjects Planned

Approximately 50 subjects will be enrolled into the study.

Main Selection Criteria

Subjects will be eligible if they meet all of the following inclusion criteria and none of the exclusion criteria:

Inclusion criteria:

- Age > 18 years
- Clinically indicated Rubidium-82 or N-13 ammonia PET study
- Ten healthy volunteers recruited using web based advertisements.
- Known coronary artery disease (prior percutaneous coronary intervention, prior coronary artery bypass surgery or Q wave MI on ECG) or intermediate to high pretest likelihood of CAD
- Able to exercise on a treadmill
- Able and willing to provide informed consent to participate in the study

Exclusion criteria:

- Contraindications to exercise stress testing such as
 - unstable angina
 - known severe left main coronary artery stenosis
 - severe or uncontrolled heart failure
 - uncontrolled atrial or ventricular arrhythmias
 - symptomatic hypotension or severe hypertension (systolic blood pressure < 90 or > 200 mmHg, respectively)
 - > 1st degree atrioventricular block in the absence of a functioning pacemaker.
- Contraindications to Lexiscan use such
 - Allergy or intolerance to aminophylline or regadenoson

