	Exercise Stress	Dipyridamole Stress	p Value	Correlation	Significance of Correlation
Summed stress score	9.1 ± 5.7	6.9 ± 5.9	<0.01	0.80	<0.001
Summed rest score	3.4 ± 3.3	3.2 ± 2.8	NS	0.79	<0.001
Summed difference score	5.8 ± 4.7	3.7 ± 4.6	<0.02	0.61	0.001
LV defect size (stress) (%)	19.3 ± 11.5	13.8 ± 13.6	<0.02	0.62	0.001
LV defect size (rest) (%)	8.1 ± 9.4	6.4 ± 6.5	NS	0.57	0.003

Values are mean ± SD.

LV = left ventricle; PET = positron emission tomography.

Myocardial count density of N-13 ammonia was significantly greater with dipyridamole compared to exercise stress. Successful performance of exercise ammonia required coordination between the cyclotron team and the imaging team. The authors concluded that treadmill exercise produces larger and more severe perfusion defects than dipyridamole and may reflect true ischemia.

III. STUDY METHODS

This is a single-center, prospective cohort study of subjects undergoing clinically indicated PET/CT MPI, with documented coronary artery disease or an intermediate to high pretest likelihood of coronary artery disease based on age gender and symptoms as described in the ACC/AHA/ASNC appropriate use criteria for cardiac radionuclide imaging.¹² Following completion of the clinical study, the research study is explained to the subjects. Consenting subjects will return on another day for a repeat stress study with Lexercise or a repeat Lexiscan stress PET. Approximately 50 subjects (not more than 16 patients with normal Rubidium-82 PETMPI and 34 with reversible perfusion defects) will be enrolled in this study. After successful screening and enrollment, 13 random subjects (8 normal and 5 ischemic) will return for repeat Lexiscan PET, and 34 subjects will return for a Lexercise PET/CT MPI, on the next calendar day or within 2 weeks of the clinical Rubidium-82 or N-13 ammonia PET study.

SUBJECT SELECTION

Main Selection Criteria

Subjects will be eligible if they meet all of the following inclusion criteria and none of the exclusion criteria:

Inclusion criteria:

- Age > 18 years
- Clinically indicated Rubidium-82 or N-13 ammonia PET study
- Ten healthy volunteers recruited using web based advertisements.

- Known coronary artery disease (prior percutaneous coronary intervention, prior coronary artery bypass surgery or Q wave MI on ECG) or intermediate to high pretest likelihood of CAD
- Able to exercise on a treadmill
- Able and willing to provide informed consent to participate in the study

Exclusion criteria:

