- Hospital in-patients with request for pharmacologic stress: Attending physicians will be asked if they felt comfortable introducing the study to their subjects that they schedule for in-patient pharmacologic stress myocardial perfusion study verbally during their visit. If the physician introduces the study verbally, the subject will be asked if they would like to speak with a coordinator after the visit. If they would like to speak with someone, the coordinator will be notified and they will explain the study to the subject and go over the inclusion and exclusion criteria for the study. If they are interested in participating in the study an appointment will be made for their first visit.
- Special attention will be paid to enroll women and minorities in the study.
- Ten healthy volunteers will be recruited for this study using web based advertisements. They will all undergo Lexiscan (regadenoson) followed by Lexercise protocol (exercise + regadenoson) on a separate day.

b) Procedures for obtaining informed consent (including timing of the consent process)

For subjects interested in speaking to a study staff, Study PI, will go over the inclusion and exclusion criteria and will describe the study and procedures to the potential subject over the phone or in person. If the subject qualifies and is interested he/she is encouraged to discuss the study with his/her primary care physician or family members. Upon arrival for the study, the subject will be given a copy of the consent form to read. After the subject has finished reading the consent form, one of the physician investigators will describe the study in detail and answer any questions or concerns

the subject might have. If the subject agrees to participate in the study they will be asked to provide his/her written informed consent. Subjects will be given a copy of the signed consent form for their records. The investigator will inform the subject that they have the alternative not to participate in the study and can withdraw their consent at any point during the study.

The subjects will be given as much as 2 weeks to consider participation in the trial. Pregnant women and minors are excluded from this trial. Subjects that are determined by the physician to be unable to consent due to their physical or mental condition will not be enrolled in this trial.

V. STUDY PROCEDURES

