Rubidium-82 or N-13 ammonia PET image acquisition:

Following skin preparation and ECG lead placement, patient undergoes a symptom limited standard Bruce exercise treadmill test. At peak exercise (when patient is unable to exercise for more than 1 minute), the treadmill is stopped and patient is immediately positioned on the imaging table. Image acquisition is started with a CT scout image for positioning the heart (10 mA, AP scout, 9 seconds). Then 0.4 mg of regadenoson is given by intravenous push over 10 seconds followed by 10 ml of normal saline flush. Right after the saline flush, 40-60 mCi of Rubidium-82 or 20 mCi of N-13 ammonia is injected and emission imaging started in a list mode fashion started at the time of injection of radiotracer. Following completion of the emission imaging, a CT transmission scan (20 mA, 120 KV, non-gated, free tidal breathing) is obtained for correction of photon attenuation by soft tissues. .

Rest and Lexiscan stress images from the clinical study and the Lexercise stress emission images will be unlisted for analysis into a static file, a gated file and dynamic image frames (36 frames of 5 seconds each, 8 frames of 15 seconds each, and 6 frames of 30 seconds each for stress and 2 groups for rest of 24 frames at 5 seconds each and 8 frames at 30 seconds each). In subjects with serious or bothersome adverse effects, aminophylline will be administered intravenously (1 mg/kg, to a maximum of 150 mg) to alleviate the symptoms.

Myocardial blood flow quantification:

Myocardial blood flow (in ml/gm/min) at rest and after vasodilator stress will be quantified using a software based on GFADS and a 2 compartment model, developed and validated at the Brigham and Women's Hospital.¹³ Rest and peak stress myocardial blood flow will be computed in ml/gm/min and global and regional (vascular territories assigned as described below) coronary flow reserve computed by dividing stress myocardial blood flow by rest myocardial blood flow. Coronary vascular resistance at rest and stress will be computed by dividing mean aortic pressure [derived as 2 (diastolic blood pressure) + systolic blood pressure/3] by myocardial blood flow. In addition to calculating the myocardial blood flow for the left ventricle as a whole, myocardial blood flow will be determined for each of three vascular beds

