- Sub diaphragmatic activity (liver heart ratios)
- Defect contrast
- Signal to noise ratio and
- Dynamic image evaluability will be assessed

VI. BIOSTATISTICAL ANALYSIS

The overall aim of this pilot study of 50 patients is to assess the tolerability, safety, diagnostic accuracy and image quality between Lexiscan with symptom limited exercise compared to Lexiscan alone.

Aim 1. For this aim, we will compare the reported side effect profile for Lexercise to Lexiscan PET, using a Pearson Chi square test. A P-value of <0.05 will be considered significant.

Aim 2: For this aim, we will compare objective measures of image quality including signal to noise ratio using dynamic Rubidium-82 images or N-13 ammonia, the frequency of misregistration between PET and CT, the frequency of presumed motion artifact and bowel radiotracer activity. These measures will be compared using a student's t-test or a Pearson Chi square test, as appropriate. A P-value of <0.05 will be considered significant.

Aim 3: For this aim, we seek to compare measures of semi quantitative relative perfusion, absolute perfusion and LVEF using the Lexiscan alone compared to Lexercise PET. Firstly, we will compare semi-quantitative defect size, severity and reversibility between the Lexercise and Lexiscan PET studies. Based on the results of one prior study using N-13 ammonia and comparing dipyridamole versus treadmill exercise², a sample size of 35 subjects with reversible defects should be adequate to identify if significant differences exist between Lexercise and Lexiscan PET protocols. Next, we will study the changes in LVEF from rest to peak stress in Lexercise versus Lexiscan PET studies in the normal and ischemic subjects. Finally, we will compare regional rest and peak stress myocardial blood flow and coronary flow reserve between Lexercise and Lexiscan PET studies.

VII. RISKS AND DISCOMFORT

Time: Participation in this trial entails an exercise vasodilator stress Rubidium-82 PET or N-13 ammonia scan. The total time spent for the study procedures is approximately 1 hour.

Intravenous line insertion: Possible side effects intravenous line insertion are pain, bruising, or infection where the needle entered the skin. Some people faint or get dizzy during insertion of the intravenous line.

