No direct benefit is anticipated to individual subjects. The results of this study may benefit society through evaluation of the diagnostic utility of novel protocol utilizing combined symptom limited exercise vasodilator stress test to image endothelium dependent and endothelium independent factors affecting myocardial blood flow.

IX. MONITORING AND QUALITY ASSURANCE

Subject safety will be ensured by strict adherence to inclusion and exclusion criteria and close monitoring. Subjects that experienced serious adverse events during the study will be removed from the study and followed up, but no other study procedures will be performed. We will monitor the subjects closely for seizures and ischemic symptoms. History of seizures is an exclusion criteria for the study. Individuals who experience seizures for the first time during the initial regadenoson study will be excluded from the second regadenoson with exercise study. Intravenous aminophylline, a competitive agonist, will be administered for ischemic symptoms. Subjects with ischemic symptoms will be monitored until complete resolution (current clinical practice). As listed in page 22, study endpoints, safety blood work will be drawn after the Lexiscan and the Lexercise PET study to measure serum troponin T levels. This study does not involve treatment and hence a data safety monitoring board.

This is a pilot clinical study of about 50 subjects. The study PI, [name], will be responsible for monitoring the study procedures after every subject is enrolled, including the accuracy and completeness of the case report form entries, source documents and informed consent after every enrollment. These documents will be appropriately maintained on submission.

Specification of Source Documents

The following information will be included in the source medical records:

- Demographic data (age, sex, and race)
- Inclusion and exclusion criteria details
- Participation in study and signed and dated informed consent forms
- Visit dates
- Medical history and physical examination details
- Key efficacy and safety data
- Adverse events and concomitant medication
- Results of relevant examinations
- Laboratory printouts
- Reason for premature discontinuation

Ethical Conduct of the Study

The investigator(s) and all parties involved in this study will conduct the study in adherence to GCP, ICH Guidelines and the applicable laws and regulations.

Subject Confidentiality

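### Side effects and yes/no image-quality measures are compared in subjects who have both scans, but the only test named is Pearson chi-square, which assumes independent observations

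*Combined protocol and SAP*

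**What the plan says.** Section numbers are those in the body of the document.

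**Tests.** For Aim 1, section VI (Biostatistical Analysis) and the Synopsis Statistical Plan both say "we will compare the reported side effect profile for Lexercise to Lexiscan PET, using a Pearson Chi square test". For Aim 2 (signal-to-noise ratio, misregistration, motion artifact, bowel activity) both offer a Student's "t-test or a Pearson Chi square test, as appropriate". The significance level is 0.05. No McNemar test, paired t-test, mixed model or other within-subject method appears anywhere.

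**Design.** Section III (Study Methods): "Consenting subjects will return on another day for a repeat stress study with Lexercise or a repeat Lexiscan stress PET". Section V, under image acquisition: "Rest and Lexiscan stress images from the clinical study and the Lexercise stress emission images will be unlisted for analysis". Section IV on the ten volunteers: "They will all undergo Lexiscan (regadenoson) followed by Lexercise protocol (exercise + regadenoson) on a separate day". Section IX on safety: "Individuals who experience seizures for the first time during the initial regadenoson study will be excluded from the second regadenoson with exercise study".

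**Numbers.** The Synopsis says "13 random subjects (8 normal and 5 ischemic) will return for repeat Lexiscan PET" and "37 subjects will return for a Lexercise PET/CT MPI". Section III gives the same 13 but 34 for Lexercise.

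**The concern.** Each Lexercise subject contributes two results to the comparison, a Lexiscan result and a later Lexercise result. Pearson chi-square would treat the 2 x 37 = 74 scans as if they came from 74 different people. If a subject who has a symptom on one scan is more likely to have it on the other, the test uses too large a standard error for the difference.

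The stake is greatest in Aim 1. Section III's rationale material presents the safety of full exercise plus Lexiscan as something still to be shown. A non-significant result from a test with too little power could be read as good tolerability. In Aim 2, Hypothesis 2 predicts more misregistration with Lexercise, which is also a yes/no outcome measured twice in the same people.

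**Working it through.** The plan states no power, effect size or sample size for Aims 1 and 2, so there is no figure of its own to reproduce here.

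**Is the design paired?** The passages quoted above put both scans in the same person. The Aim 3 sample sizes point the same way. From the N-13 ammonia table in the rationale for Aim 3, SD of difference = sqrt(s1² + s2² - 2·r·s1·s2):
- Summed stress score: sqrt(5.7² + 5.9² - 2·0.80·5.7·5.9) = 3.67. For a difference of 9.1 - 6.9 = 2.2, a paired t-test (two-sided 5%, 80% power assumed) needs 24 pairs. The Synopsis states 24.
- Stress defect size: sqrt(11.5² + 13.6² - 2·0.62·11.5·13.6) = 11.10. For 19.3 - 13.8 = 5.5, it needs 34 pairs. Section VI states 35.
- Unpaired, the same inputs need 110 and 83 per group.

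The plan does not show its method, so this supports pairing but does not prove it.

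**Inputs for Aims 1 and 2.** Pairs: 37 or 34. Lexiscan rate: 28%, the dyspnea rate in section VII. Assumed, because the documents do not give them: phi, the Lexercise rates, and both misregistration rates.

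**Size by hand.** With the same rate p on both scans, the true variance of the difference is 2p(1-p)(1-phi)/n, while Pearson uses about 2p(1-p)/n. The true size is therefore about P(|Z| > 1.96/sqrt(1-phi)). At phi 0.3: 1.96/0.837 = 2.34, giving 1.9%. At phi -0.2: 1.96/1.095 = 1.79, giving 7.4%.

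**Exact enumeration.** The share with the event on both scans is a = p1·p2 + phi·sqrt(p1(1-p1)p2(1-p2)). The other cells are p2 - a (Lexercise only), p1 - a (Lexiscan only) and the remainder. For 28% versus 50% at phi 0.3: a = 0.14 + 0.3·0.2245 = 0.207, Lexercise only 0.293, Lexiscan only 0.073, neither 0.427. Every possible paired 2x2 table was weighted by its multinomial probability and tested at 0.05 with uncorrected Pearson and with mid-p McNemar.

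True size, 28% on both scans:

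| phi | -0.2 | 0 | 0.2 | 0.3 | 0.5 |
|---|---|---|---|---|---|
| Pearson, 37 pairs | 7.4% | 5.1% | 2.9% | 2.0% | 0.6% |
| Pearson, 34 pairs | 7.8% | 5.4% | 3.2% | 2.2% | 0.7% |

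Mid-p McNemar stays between 3.5 and 4.7% throughout.

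Power, Pearson / mid-p McNemar:

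| Lexiscan vs Lexercise | phi 0 | 0.2 | 0.3 | 0.5 |
|---|---|---|---|---|
| 28% vs 50%, 37 pairs | 49 / 47% | 48 / 57% | 48 / 62% | 48 / 78% |
| 10% vs 30% (misregistration), 37 pairs | 59 / 56% | 60 / 65% | 61 / 71% | 62 / 88% |
| 5% vs 15%, 37 pairs | 32.5 / 24.5% | 30.2 / 27.0% | 29 / 28% | 24.8 / 30.6% |

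With 34 pairs and 28% vs 50%, Pearson has 45-48% and mid-p 44, 52, 58 and 74%.

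**One table as an example.** 37 pairs: both 8, Lexercise only 8, Lexiscan only 1, neither 20. That is 16/37 versus 9/37. Pearson: chi-square 2.96, p = 0.085. Exact McNemar on 8 versus 1: 2·(1 + 9)/512 = 0.039. Mid-p: 0.039 - 9/512 = 0.021.

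**The comparison for which Pearson is valid.** Lexercise return visits against the 13 repeat-Lexiscan return visits involve different people. Enumerating two independent binomials, 37 versus 13 has size 5.0% and power 26% for 50% versus 28%. For 34 versus 13 the figures are 5.4% and 28%. Without the ten volunteers, 27 versus 13 gives 5.1% and 25%.

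**The case against.** The strongest defence is that the plan means the return-visit comparison. A random 13 repeat Lexiscan while the others have Lexercise, so the groups are different people and Pearson holds its level. Some procedures fit this. Patients have the research study explained after the clinical scan, and volunteers have no blood drawn at their Lexiscan visit, so troponin after Lexiscan fits the repeat-Lexiscan visit best. This comparison would also avoid the order problem. However, no section defines it. It would discard the clinical Lexiscan images that section V says are analysed. No volunteer could be a control, and power would be about 26%. Pooling all 50 + 13 = 63 Lexiscan scans against 37 is not independent either, although its power for 28% versus 50% (60-62%) is matched or beaten by mid-p only from about phi 0.3, and clearly only at 0.5.

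The second defence is that the harm depends on an unknown phi and on common events. That stands. At phi 0 there is no gain. For 5% versus 15%, mid-p has less power than Pearson at phi 0 and 0.2, about the same at 0.3, and more only at 0.5. Apart from dyspnea (28%) and headache (26%), every effect listed in section VII is at 16% or below. For 13% versus an assumed 25%, mid-p has 23, 27 and 30% at phi 0, 0.2 and 0.3, against 26, 24 and 22% for Pearson.

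Third, this is a pilot with no power claim for Aims 1 and 2, and with positive phi the error is conservative. That limits the weight of the point but does not make the test fit the design.

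**Conclusion.** The point holds: for the within-subject comparison that the documents describe, the named test does not fit, whatever phi is. How much it matters depends on phi and on the event rates, which are assumed here. With positive phi (plausible, but not documented), Pearson is conservative: size 2.9% to 0.6% at phi 0.2 to 0.5, and 9 to 30 points less power than mid-p McNemar for 28% versus 50% (57 - 48 and 78 - 48). With negative phi it is liberal (7.4% at -0.2). The t-test is a lesser matter: the plan does not say whether it is paired, so it is unspecified rather than wrong.

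Three stronger readings are tempting, and the documents do not support them:
- **That Pearson inflates false positives here.** It does so only if phi is negative.
- **That any paired test is better.** Mid-p can lose power for rare effects. Exact McNemar has less power than Pearson at 28% versus 50% for phi 0 and 0.2 (40 and 48%, against 49 and 48%), and at 5% versus 15% at every phi checked (16-17%).
- **That the plan drops subjects whose Lexiscan was withheld during exercise, and so flatters Lexercise.** No section says they are dropped or gives the number expected. How they are counted is a missing detail, and any size put on it would be speculation.

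This should be fixed before analysis. It does not undermine the design.

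**What to change.** In section VI and in the Synopsis Statistical Plan:
1. State that the primary Lexercise versus Lexiscan comparison in Aims 1 and 2 is within subject.
2. Replace Pearson chi-square with mid-p McNemar. Report the paired difference in proportions with a 95% CI, and rely on the interval for rare effects.
3. State that the t-test is paired.
4. Keep the 13 Lexiscan-Lexiscan subjects out of that comparison. Use them separately to describe repeatability and any order effect, because Lexiscan always comes first and McNemar cannot separate order from protocol.
5. Report how many subjects had Lexiscan withheld during exercise, and their symptoms. The section V datasheet already records symptoms and why the test ended.
6. Reconcile 37 with 34.

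The cost is a few sentences, with no extra subjects or scans. The downside is some loss of power if phi is near zero or the effect is rare.

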Aim 2: For this aim, we will compare objective measures of image quality including signal to noise ratio using dynamic Rubidium-82 or N-13 ammonia images, the frequency of misregistration between PET and CT, the frequency of presumed motion artifact and bowel radiotracer activity. These measures will be compared using a student's t-test or a Pearson Chi square test, as appropriate. A P-value of <0.05 will be considered significant.

Aim 3: For this aim, we seek to compare measures of semi quantitative relative perfusion, absolute perfusion and LVEF using the Lexiscan alone compared to Lexercise PET. Firstly, we will compare semi-quantitative defect size, severity and reversibility between the Lexercise and Lexiscan PET studies. Based on the results of one prior study using N-13 ammonia and comparing dipyridamole versus treadmill exercise², a sample size of 24 subjects with reversible defects should be adequate to identify if significant differences exist between Lexercise and Lexiscan PET protocols. Next, we will compare the differences in regional rest and peak stress myocardial blood flow and coronary flow reserve in the defect territory compared to normal territory between the Lexercise and Lexiscan protocols. Finally, we will study the changes in LVEF from rest to peak stress in Lexercise versus Lexiscan PET studies in the normal and ischemic subjects.

[figure not shown]
I. BACKGROUND:

Myocardial perfusion imaging (MPI) with positron emission tomography (PET) is more accurate than single photon emission computed tomography (SPECT)³, enables non-invasive quantitation of absolute myocardial blood flow (MBF), and is particularly helpful in the obese individuals and those that are unable to exercise.³ Presently PETMPI is indicated only for subjects that are unable to exercise⁴,

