(left anterior descending [LAD], left circumflex [LCx], and right coronary artery [RCA]). Subendocardial and subepicardial myocardial blood flow will be assessed globally.

Interpretation of relative myocardial perfusion images:

The semi-quantitative clinical interpretation of Rubidium-82 or N-13 ammonia images will be performed using a standard 17 segment model and a 0-4 scale (0=normal, 1= mild defect, 2=moderate defect, 3=severe defect, 4= absent radiotracer uptake). The sum of the scores in the 17 segments at stress and rest will be computed as the summed stress score (SSS) and summed rest score (SRS) respectively. The summed difference scores (SDS) will be derived as SSS – SRS. The SSS, SRS and SDS will be converted into percentages to compute total percent myocardium abnormal, scarred or ischemic determined as $(100/68)*SSS$, $(100/68)*SRS$ or $(100/68)*SDS$, respectively. Perfusion defects on relative PET will be assigned vascular distributions as described previously.¹⁴ LV volumes and EF will be estimated using FDA approved software (EcTb), with automatic edge detection and manual refinement when needed.

Interpretation of absolute myocardial perfusion images:

Myocardial blood flow at rest, stress and CFR are calculated for the left ventricle as a whole, as well as for each of three vascular beds (left anterior descending [LAD], left circumflex [LCx], and right coronary artery [RCA]). Polar plots of CFR will be generated and defect extent and severity computed in relation to a quantitative CFR normal limits database (developed at BWH).

Study Endpoints Assessed:

- Diagnostic value:
 - Defect size, severity, extent and contrast with Lexiscan alone compared to exercise Lexiscan protocol
 - Left ventricular ejection fraction at rest and immediately post stress will be compared in the Lexiscan alone and the exercise Lexiscan protocol.
 - Myocardial blood flow estimates and coronary flow reserve will be compared between the Lexiscan alone and Lexercise protocols.
 - Comparison to coronary angiography results when available.
- Safety and tolerability:
 - Side effects, ECG changes, blood pressure changes, will be recorded.
 - Safety blood work will be drawn after the Lexiscan and the Lexercise PET study to measure serum troponin T levels.
 - Radiation dose to the staff will be measured using personal dosimeters after the Lexiscan as well as the Lexercise PET study.
- Image quality:

- Motion artifacts
- Image registration

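### No primary comparison is named: five tests carry an unadjusted P<0.05, and the sample-size sentence does not say which defect measure it serves

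*Combined protocol and SAP*

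**What the plan says.** The statistical text appears twice, in the Synopsis (Statistical Plan) and in Section VI, Biostatistical Analysis. Aims 1 and 2 agree in substance; Aim 3 does not.

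- **Aim 1:** "we will compare the reported side effect profile for Lexercise to Lexiscan PET, using a Pearson Chi square test", with significance at 0.05.
- **Aim 2:** signal-to-noise ratio plus "the frequency of misregistration between PET and CT, the frequency of presumed motion artifact and bowel radiotracer activity". The list is open-ended. The tests are t-test or chi-square, "as appropriate. A P-value of <0.05 will be considered significant".
- **Aim 3:** "Firstly, we will compare semi-quantitative defect size, severity and reversibility between the Lexercise and Lexiscan PET studies". Section VI adds "the changes in LVEF from rest to peak stress in Lexercise versus Lexiscan PET studies in the normal and ischemic subjects" and then "Finally, we will compare regional rest and peak stress myocardial blood flow and coronary flow reserve between Lexercise and Lexiscan PET studies". No test and no significance level is given for Aim 3. The Synopsis words the flow comparison differently, as defect territory against normal territory.
- **Sample size:** placed straight after the three defect measures, the sentence says the number "should be adequate to identify if significant differences exist between Lexercise and Lexiscan PET protocols". The number is 24 in the Synopsis and 35 in Section VI. No measure, effect, standard deviation, power or sidedness is given.
- **Endpoints:** Section V, Study Endpoints Assessed, groups the endpoints under diagnostic value, safety and image quality. The first entry is "Defect size, severity, extent and contrast with Lexiscan alone compared to exercise Lexiscan protocol". None is marked primary or secondary.

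The study is called a pilot in several places.

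**The concern.** A plan that sets a significance rule should say which comparison it is for. Here the rule covers several image-quality measures and the side-effect profile, all at the full 0.05, so the chance of some false claim of a difference exceeds the stated 5%. Aim 3, the diagnostic question, has three defect measures that can disagree (severity might differ while reversibility does not), and nothing says which one answers it. A claim that the sample is adequate cannot be checked until its measure is known, and this document gives two different numbers for it.

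**Working it through.** **Chance of at least one false positive.** Assume all null hypotheses are true and each test is two-sided at 0.05 (the plan does not state sidedness). For k independent tests the chance is 1 − 0.95^k. For correlated tests it was simulated with equally correlated z-tests.

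Counts, taken from Section VI:
- 5 tests: Aim 1 as one chi-square, plus the four named Aim 2 measures. Only these have a stated 0.05 rule.
- 10 tests: add three defect measures and LVEF change in two groups (1 + 4 + 3 + 2), assuming 0.05 for Aim 3.
- 13 tests: add rest flow, stress flow and CFR, each counted once, under the same assumption.

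| Tests | Independent | Correlation 0.5 | Correlation 0.8 |
|---|---|---|---|
| 5 | 1 − 0.95^5 = 22.6% | 18% | 13% |
| 10 | 1 − 0.95^10 = 40.1% | 29% | 17% |
| 13 | 1 − 0.95^13 = 48.7% | 33% | 19% |

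**What the sample-size sentence can mean.** Neither 24 nor 35 can be reproduced from stated inputs, because the measure, power and sidedness are missing. The sentence describes an N-13 ammonia study of dipyridamole against treadmill exercise. The protocol reproduces such a study's results in its Table 3 (26 patients), so those figures are used. (The sentence cites reference 2, which is the rubidium-82 study; the N-13 study is reference 8.)

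Each patient has both scans, so the analysis is paired. The SD of the difference is √(s1² + s2² − 2·r·s1·s2), and the standardised effect dz is the mean difference divided by that SD.

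- Summed stress score: difference 9.1 − 6.9 = 2.2; SD = √(5.7² + 5.9² − 2·0.80·5.7·5.9) = √13.49 = 3.67; dz = 0.60.
- Summed difference score: difference 5.8 − 3.7 = 2.1; SD = √(4.7² + 4.6² − 2·0.61·4.7·4.6) = √16.87 = 4.11; dz = 0.51.
- Stress LV defect size: difference 19.3 − 13.8 = 5.5; SD = √(11.5² + 13.6² − 2·0.62·11.5·13.6) = √123.27 = 11.10; dz = 0.50.

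Check against the table: t = dz·√26 gives 3.05, 2.61 and 2.53, so P = 0.005, 0.015 and 0.018. These agree with the printed <0.01, <0.02 and <0.02.

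Power of a two-sided paired t-test at 0.05 (noncentral t):

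| Measure | 19 pairs | 24 pairs | 35 pairs | Pairs for 80% | Pairs for 90% |
|---|---|---|---|---|---|
| Summed stress score | 70% | 80% | 93% | 24 | 32 |
| Summed difference score | 56% | 67% | 84% | 33 | 43 |
| Stress LV defect size | 53% | 64% | 81% | 34 | 45 |

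The 19-pair column applies if the five ischemic subjects assigned to repeat Lexiscan come out of the Synopsis's 24: 24 − 5 = 19.

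So 24 is the 80% number for summed stress score, while 35 is close to the 80% number for the other two (33 and 34). This does not prove how either figure was chosen. It does show that the missing measure changes the answer.

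**The case against.** The strongest reply is that this is a 50-subject pilot, for which strict error control is often not expected. The all-null assumption is also harsh: the prior exercise-versus-dipyridamole data in the protocol already show differences in gut ratio and defect scores. And the hypotheses do not all favour Lexercise. Hypothesis 2 expects more misregistration with it, so some false positives would count against it. All of this stands and limits the harm. It does not remove the point, because the plan declares significance and claims adequacy instead of confining itself to estimation.

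Four stronger readings are tempting and not supported:

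- A reader might infer that each side effect is tested at its own 0.05. Aim 1 names one chi-square on the profile, and it is counted as one test here.
- A reader might infer that a false positive is likely. The five tests with a stated level stay at or below 23%, and the 13-test count stays below 50% even under independence. Passing 50% needs further splitting, for example by vascular bed, that the text does not prescribe, and a level for Aim 3 that it does not state.
- A reader might infer that the adequacy claim holds for one defect measure and fails for the others. At an 80% bar, itself assumed, that is so at 24. At Section VI's 35 all three measures pass.
- A reader might infer that the sample-size sentence is attached to nothing. Its position ties it to the defect measures; what is missing is which one.

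It is also fair to say that summed stress score is not the only sensible choice. Hypothesis 3 speaks of defect contrast and regional CFR, and the sponsor may prefer another measure.

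**Conclusion.** The point holds in this limited form. No comparison is primary. The five tests under the explicit 0.05 rule carry a 13% to 23% chance of at least one false positive (correlation 0.8 down to 0, all nulls true). If 0.05 is also assumed for Aim 3, the range is roughly 17% (10 tests, correlation 0.8) to 49% (13 independent tests).

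The adequacy claim depends on an unnamed measure and on which of two numbers is meant: 64% to 80% power at 24, 81% to 93% at 35, and 53% to 70% if only 19 ischemic subjects supply pairs. The power figures assume that the prior exercise-versus-dipyridamole effects and correlations carry over to Lexercise versus Lexiscan, which the documents do not establish. Given the pilot setting, this is a cheap improvement and not a threat to the study.

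**What to change.** In both the Synopsis and Section VI:

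1. Name one primary measure: a within-patient Lexercise-minus-Lexiscan difference in a defect measure, in patients with reversible defects, tested at two-sided 0.05. One candidate is percent myocardium abnormal at stress, (100/68) × SSS, already defined in Section V. It is SSS rescaled, so the SSS power figures apply to it.
2. Reconcile 24 with 35. State the power for the chosen measure at the number of ischemic subjects who actually undergo Lexercise, after removing those sent to repeat Lexiscan.
3. For the other efficacy and image-quality comparisons, replace the blanket 0.05 rule with estimates and 95% confidence intervals labelled exploratory. If any are to be called significant, apply Holm within the aim.
4. Report Aim 1 safety as estimates with 95% confidence intervals and no multiplicity penalty, so that sensitivity to harm is not reduced.

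The cost is wording only, with no new data collection or procedures. If the power in step 2 turns out low, the adequacy claim should be softened to match. The downside is that secondary measures can no longer be called significant at an unadjusted 0.05.
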